9.4. Pattern Mixture Model

Patients are classified into four patterns for missing 6-MWT/KCCQ-OS data during the DB period:

1. Patients who died (including HT and LVAD placement) or unable to walk due to progression of ATTR amyloidosis (including hospitalization due to ATTR amyloidosis; applicable to 6-MWT only) before Month 30 visit: the missing change from baseline values at a postbaseline visit will be imputed as sampling with replacement from the worst 10% of observed change from baseline values from all patients at the same visit

and in same treatment group and same baseline tafamidis group, capped by the worst possible change for the patient (i.e. 0 – baseline value).

2. Patients in the vutrisiran arm who are not in Pattern 1 and have missing visits within 126 days of the last dose of vutrisiran: the missing change from baseline values are considered MAR and will be imputed using multiple imputation (MI) estimated from vutrisiran patients with non-missing data collected on treatment (i.e., data on visits within 126 days from last dose) in the same baseline tafamidis group. The window of 126 days is chosen as $1.5 \times$ the dosing interval of 84 days.
3. Patients in the vutrisiran arm who are not in Pattern 1 and have missing visits that are more than 126 days after the last dose of vutrisiran:
 - a. If there are sufficient (i.e., at least 10) retrieved dropouts at Month 30 in the same baseline tafamidis group, i.e., vutrisiran patients who discontinued treatment but still had assessment that are more than 126 days after the last dose, the missing data will be imputed using data from these retrieved dropouts.
 - b. If there are insufficient retrieved dropouts, missing change from baseline values will be assumed to be MNAR and imputed (using data from placebo patients in the same baseline tafamidis group) using the copy reference (CR) approach.
4. Patients in the placebo arm who are not in Pattern 1 and have missing data for other reasons:
 - a. If there are sufficient (i.e., at least 10) retrieved dropouts at Month 30 in the same baseline tafamidis group, i.e., placebo patients who discontinued study treatment but still had assessment that are more than 126 days from the last dose, the missing data will be imputed using data from these retrieved dropouts.

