 - b. If there are insufficient retrieved dropouts, missing change from baseline values will be considered as MAR and imputed using MI estimated from all placebo patients in the same baseline tafamidis group.

Imputed change from baseline from any of the above methods will be capped by the worst possible change of the patient (0 – baseline value).

Details of MI:

For patients in Pattern 1, the imputation details are described above. For patients in Pattern 2 and Pattern 4b, all missing data for the placebo arm and missing data for the vutrisiran arm during the on-treatment period (ie, assessments within 126 days of the last dose of study drug) will be imputed using MI under the MAR assumption. Since the pattern of missing data within patients may be non-monotone, multiple imputation will be conducted separately by treatment arm and baseline tafamidis use group using the Markov Chain Monte Carlo (MCMC) method. For each treatment arm/baseline tafamidis use group, the imputation model will include type of amyloidosis (hATTR vs. wtATTR), NYHA class (I/II vs. III), age at randomization (<75 vs. ≥ 75), NT-proBNP (≤ 3000 ng/L vs > 3000 ng/L), baseline value, and all post baseline change from baseline values at protocol specified visits. The input dataset DATAIN will exclude data from vutrisiran patients that were collected after treatment discontinuation (ie, more than 126 days after the last dose of study drug). Below is a sample SAS code for the multiple imputation:

```
proc mi data=DATAIN out=DATA_STEP1 seed=xxx n impute=100;
  by treatment bltaf;
  em maxiter=300 converge=1e-4 itprint outem=outem;
  var baseline_variables base chg6m chg12m chg18m chg24m chg30m;
  mcmc chain=multiple initial=em;
run;
```

The MI procedure generates imputed values for all missing values. For patients in Pattern 1, the imputed data will be discarded and replaced by the imputed values using method described in Pattern 1 above. For vutrisiran patients, the imputed data from the on-treatment period will be kept while the imputed data after treatment discontinuation will be discarded and replaced by either the observed non-missing values (if available) or the imputed values using the CR approach described below (Pattern 3b). The imputation model is the same as that for Pattern 2 and 4.

```
proc mi data=DATA_STEP1_2 out=DATA_STEP2 n impute=1 seed=xxxx;
  by _imputation_ bltaf;
  class treatment;
  fcs nbiter=30 reg (chg30m = baseline_variables base chg6m chg12m chg18m
  chg24m);

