  mnar model (chg30m / modelobs=(treatment='placebo'));
  var baseline_variables base chg6m chg12m chg18m chg24m;
run;
```

For imputation using the retrieved dropouts (Pattern 3a and 4a), the multiple imputation approach described in [Wang 2022] is adopted.

Combining Results

Missing values will be imputed 100 times to generate 100 complete datasets using the procedures described above (via MI, CR or other methods described above). An analysis of covariance (ANCOVA) model will be fit to each imputed dataset for the change from baseline in 6-MWT/KCCQ-OS at Month 30. The ANCOVA model will include baseline 6-MWT/KCCQ-OS as a covariate and treatment arm, baseline tafamidis use, treatment by baseline tafamidis use interaction, ATTR disease type, and age group as factors. For the vutrisiran monotherapy subgroup analysis, baseline tafamidis use, and treatment by baseline tafamidis use interaction will be removed from the model. The LS mean and SE estimated from the ANCOVA model fit to each imputed dataset will be combined by applying Rubin's rules,[Rubin 1996; Rubin 1987] using SAS PROC MIANALYZE to produce inferential results including the treatment difference in LS means, 95% CI for the treatment difference, and the p-value.

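### SAP 9.4: the copy-reference code applies the placebo model to Month 30 only, although the text applies it to every missing off-drug visit, so this fallback is somewhat less conservative than described

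*SAP*

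**What the plan says.** SAP 9.4 sorts missing 6-MWT and KCCQ-OS data into four patterns. Pattern 3 covers vutrisiran patients' missing visits more than 126 days after the last dose. If a baseline tafamidis group has fewer than 10 retrieved dropouts at Month 30, Pattern 3b applies and the missing changes are "imputed (using data from placebo patients in the same baseline tafamidis group) using the copy reference (CR) approach". Nothing limits this to Month 30.

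Under Details of MI there are two steps. In the first, "multiple imputation will be conducted separately by treatment arm and baseline tafamidis use group using the Markov Chain Monte Carlo (MCMC) method". For vutrisiran patients, "the imputed data after treatment discontinuation will be discarded and replaced by either the observed non-missing values (if available"), or otherwise by copy-reference values. The second step is given as SAS code:

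- The imputation regression names one target: "fcs nbiter=30 reg (chg30m = baseline_variables base chg6m chg12m chg18m" and then `chg24m`.
- The placebo restriction names the same single target: "mnar model (chg30m / modelobs=(treatment='placebo".
- The variable list is "var baseline_variables base chg6m chg12m chg18m chg24m", without `chg30m`.
- The grouping is "by _imputation_ bltaf", so both arms sit in the same group.

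The completed data are analysed by ANCOVA at Month 30.

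**The concern.** The text and the code describe different imputations. The ANCOVA uses Month 30 only, but the Month 30 value is imputed by a regression on Months 6 to 24. For a patient who stopped early, several of those earlier visits are also off drug and may be missing. The text sends them to the placebo model; the code does not. Under fully conditional specification (FCS), a variable in VAR without its own model gets the default regression on the other VAR variables. Here that regression is fitted to both arms together and has no treatment term. The values it produces lie partway between the arms, and the placebo model for Month 30 then takes them as input.

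At stake is how far this analysis can be relied on. Copy reference is the fallback that asks whether the 6-MWT and KCCQ-OS results survive loss of benefit after stopping drug. If some benefit leaks back in, the test is milder than the SAP says.

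**Working it through.** **Which visits are affected.** Dosing is every 84 days, and 1.5 x 84 = 126 reproduces the SAP's window. Target days in SAP Table 4 are 169, 337, 505, 757 and 925 for Months 6, 12, 18, 24 and 30.

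- Last dose Day 1: Month 6 is 169 - 1 = 168 days later, so all five visits are off drug.
- Last dose Day 589: Month 24 is 757 - 589 = 168 days later, so Months 24 and 30 are off drug.
- Last dose Day 673: Month 24 is 84 days later (on drug) and Month 30 is 252 days later, so only Month 30 is off drug.
- Last dose Day 757: only Month 30 is off drug (168 days).

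Code and text therefore differ in effect only for last doses up to Day 589 with earlier off-drug visits missing.

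**Inputs that the documents do not give (assumed).** 6-MWT change at Month 30 of -72 m on placebo and -41 m on vutrisiran (effect 31 m); SD 80 m at each visit; equal arms; few stoppers; five visits treated as equally spaced; correlation AR(1) 0.85, AR(1) 0.7 or exchangeable 0.7. Effect at the five visits as a share of 31 m: linear (0.2, 0.4, 0.6, 0.8, 1), constant (1 throughout) or plateau at Month 18 (1/3, 2/3, 1, 1, 1).

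**Formulas.** Write x for the expected deviation from the placebo mean, d for the vector of treatment effects and S for the within-arm covariance. The on-drug visits of the stopper are set to d.

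- True copy reference: each missing visit j in turn is x_j = S(j, earlier) S(earlier, earlier)^-1 x(earlier).
- As coded, with `chg30m` added to VAR so that Month 30 can be imputed: each missing visit before Month 30 is x_j = d_j/2 + C(j, others) C(others, others)^-1 [x(others) - d(others)/2], where C = S + dd'/4 is the pooled covariance. Month 30 is the placebo regression on Months 6 to 24. The cycle is repeated 30 times, as `nbiter=30` asks.

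**One case in full.** AR(1) 0.7, linear effect, last on-drug visit Month 6. The Month 6 effect is 0.2 x 31 = 6.2 m. True copy reference carries 0.7^4 x 6.2 = 0.240 x 6.2 = 1.5 m (4.8% of 31 m), giving -72 + 1.5 = -70.5 m. The coded recursion settles at 11.6%, or 0.116 x 31 = 3.6 m, giving -68.4 m. The excess is 11.6 - 4.8 = 6.8%, about 2.1 m.

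**Excess over true copy reference, % of the Month 30 effect** (AR 0.85 / AR 0.7 / exchangeable 0.7):

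| Last on-drug visit | Linear | Constant | Plateau at Month 18 |
|---|---|---|---|
| Month 6 | 2.7 / 6.8 / 4.8 | 4.4 / 10.5 / 8.6 | 21.4 / 18.0 / 15.6 |
| Month 12 | 1.8 / 5.0 / 5.9 | 2.5 / 7.1 / 3.4 | 12.8 / 12.6 / 10.8 |
| Month 18 | 0.8 / 2.5 / 3.5 | 1.0 / 3.3 / 1.2 | 1.0 / 3.2 / 4.0 |
| Month 24 | 0 | 0 | 0 |

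SDs of 60 or 100 m change the Month 6 row by no more than about 0.2 points. For a patient with no on-drug assessment the direction is not fixed: the same recursion gives -23% to +7% for a linear effect, 20-37% for a constant one and 6-24% for a plateau.

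**Effect on the treatment difference.** This is the per-patient excess times the share of vutrisiran patients in Pattern 3b with missing off-drug visits before Month 30. The documents give no such share. At an assumed 5-10%, the shift runs from 0.03 x 31 x 0.05 = 0.05 m to 0.21 x 31 x 0.10 = 0.65 m, against 31 m.

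**The case against.** The strongest reply is that the prose governs and the code is illustrative. The prose already requires copy reference at every missing off-drug visit, requires first-step values after discontinuation to be dropped, and says the imputation model is the one used for Patterns 2 and 4, which includes all post-baseline visits. On that view the method is specified and only the listing is wrong. This stands as a description of the defect: it is a mismatch, not a poor choice of method. It does not remove the need to correct it, because the listing is the only operational account of the copy-reference step.

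It can also be said that any programmer must edit the block, since its target is not in VAR. That is true, but adding `chg30m` alone makes the step look complete while Months 6 to 24 still lack placebo terms.

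Two larger readings are tempting. A reader might infer that first-step vutrisiran values stay in as predictors. For a linear effect and a last on-drug visit at Month 6, the excess would then be about 31-58% of the effect. The discard rule excludes this. A reader might also compute the pooled fill without `chg30m` predicting the earlier visits, which gives 16-29% in the same setting. That describes a step that does not list its own target. Once `chg30m` is in VAR it helps predict the earlier visits, and in that setting the excess falls to 3-7%.

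The scope is narrow, and that also stands. Pattern 3b needs fewer than 10 retrieved dropouts, Protocol 4.3.1 encourages patients who stop drug to continue assessments, and deaths and inability to walk due to disease progression go to Pattern 1. Some carry-over from observed on-drug visits is inherent in copy reference and is already subtracted above.

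**Conclusion.** The mismatch is real: as printed, the code does not carry out the rule in the text. With `chg30m` added to VAR and nothing else changed, a patient last seen on drug at Month 6 keeps about 3-10% of the Month 30 effect beyond true copy reference if the effect is linear or constant, and 16-21% if it plateaus at Month 18. For last on-drug visits at Months 12 to 18 the excess is about 1-13%. These figures rest wholly on assumed means, SD and correlations. The shift in the treatment difference is likely small and depends on how many patients fall in Pattern 3b.

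A reader might infer that the 6-MWT and KCCQ-OS results themselves, or the multiplicity-controlled tests, are affected. They are not: the primary MMRM analyses do not use this step. Nor do the documents show that the flaw would turn a fragile result into an apparently robust one. It is a minor correction to one sensitivity analysis of two secondary endpoints.

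**What to change.** In the second-step code of SAP 9.4:

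- List `chg6m`, `chg12m`, `chg18m`, `chg24m` and `chg30m` in VAR, in visit order.
- Give each of the five its own regression on baseline variables and earlier visits only, and its own placebo MNAR MODEL term.
- State that `DATA_STEP1_2` is built by the existing discard rule: first-step values at off-treatment visits set to missing, observed off-treatment values restored, on-treatment imputed values kept.

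This costs a few lines of code and one sentence. No data collection, design feature or other analysis changes.

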The first dose of study drug should be administered in the clinic on Day 1 of the DB Period (placebo or vutrisiran 25 mg) and Day 1 of the OLE Period (vutrisiran 25 mg). If a patient has tolerated at least 1 dose of study drug in the clinic, subsequent dosing for the remainder of that period may be administered outside the study center (eg, the patient's home) at all other timepoints where allowed by applicable country and local regulations. In these cases, dosing should be administered by a trained healthcare

professional, with oversight by the Investigator. If the patient is unable to come to the study center, and a visit by a home healthcare professional is not possible due to circumstances related to the COVID-19 pandemic, q3M regimens of study drug (placebo or 25 mg vutrisiran) may be administered by the patient or the caregiver under the oversight of the Investigator, and following consultation with the medical monitor, as allowed by applicable country and local regulations. In such cases, the patient or caregiver must receive appropriate training on study drug administration. This measure is intended to remain in effect only during periods of time when the COVID-19 pandemic impedes the ability of patients to travel to the study site or healthcare professionals to go to patients' homes for dosing.

Reference Treatment, Dose, and Mode of Administration

The control drug for this study will be a placebo (sodium chloride 0.9% w/v for SC administration), which will be administered at the same dosing interval and volume as the study drug.

Duration of Treatment and Study Participation

The planned duration of treatment for each patient is up to approximately 60 months (approximately 5 years), inclusive of the 30 to 36-month DB Period and a 24-month OLE Period.

The estimated total time on study for each patient is up to approximately 6 years, including a Screening Period of up to 45 days, a DB Period of up to 36 months, an OLE Period of up to 24 months, and a Follow-up Period of up to 1 year after the last dose of study drug (18 months for women of child-bearing potential).

Statistical Methods

For the DB Period, randomization (1:1) will be stratified by: 1) baseline tafamidis use (yes versus no); 2) ATTR disease type (hATTR versus wtATTR amyloidosis with cardiomyopathy); and 3) New York Heart Association (NYHA) Class I or II and age <75 years versus all other.

[figure not shown]

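### The pattern-mixture ANCOVA for 6-MWT and KCCQ-OS leaves out NYHA class and NT-proBNP group, which its own imputation model uses: a small, avoidable loss of precision in a sensitivity analysis

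*SAP*

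**What the plan says.** SAP 9.4, under Combining Results, gives the analysis model in full. It opens with "The ANCOVA model will include baseline 6-MWT/KCCQ-OS as a covariate and treatment arm, baseline tafamidis use", goes on to the treatment-by-tafamidis interaction, and ends with "ATTR disease type, and age group as factors". For the monotherapy subgroup, "baseline tafamidis use, and treatment by baseline tafamidis use interaction will be removed from the model", and nothing is added in their place. The passage shows no redaction mark, so the list can be taken as complete.

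Earlier in the same appendix, under Details of MI, "the imputation model will include type of amyloidosis (hATTR vs. wtATTR), NYHA class (I/II vs. III), age at randomization". The list goes on to NT-proBNP (≤3000 vs >3000 ng/L), the baseline value and all post-baseline changes. Imputation is run separately by treatment arm and baseline tafamidis use. For the copy-reference step (Pattern 3b) the SAP adds: "The imputation model is the same as that for Pattern 2 and 4".

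The third stratification factor in the Protocol (Synopsis, Statistical Methods, and Section 3.5) is "New York Heart Association (NYHA) Class I or II and age <75 years versus all other". SAP 2.4 repeats it.

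**The concern.** A factor used in stratified randomisation is normally carried into the analysis model, because a model that leaves out a prognostic stratification factor tends to report too large a standard error. Age group alone does not recover the third factor here. Below age 75, patients in NYHA I/II and patients in NYHA III were randomised in different strata, and this ANCOVA does not separate them.

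The SAP also treats both omitted variables as ordinary model covariates elsewhere. SAP 5.7 includes them when it sets out covariate categories. SAP 4.7 imputes one missing baseline NT-proBNP value because that variable enters the models. The Poisson and joint frailty models in SAP 5.7.1.3 carry both. No reason is given for leaving them out of 9.4.

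At stake is the precision of the missing-not-at-random check on two secondary endpoints in the testing hierarchy. A needlessly wide interval there makes the check slightly less informative.

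**Working it through.** **Comparing the two models in SAP 9.4**

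| Baseline term | Imputation model | ANCOVA |
|---|---|---|
| Baseline 6-MWT/KCCQ-OS | yes | yes |
| ATTR disease type | yes | yes |
| Age group (<75 vs ≥75) | yes | yes |
| NYHA class (I/II vs III) | yes | no |
| NT-proBNP group (≤3000 vs >3000 ng/L) | yes | no |
| Treatment, tafamidis use | by-groups | factors (tafamidis terms in the overall model only) |

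The difference in baseline factors is NYHA class and NT-proBNP group. The listed imputation model covers Patterns 2, 3b and 4b. Pattern 1 resamples from the worst 10% of observed changes, and Patterns 3a and 4a use a separately cited retrieved-dropout method.

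**Size**

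No sample size, power or alpha figure in the documents depends on this point, so there is nothing to reproduce. Let d be the share of the ANCOVA's residual variance that the two factors would explain. The documents do not give d, so it is assumed. With complete data:

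- SE without the factors ÷ SE with them = 1/√(1 − d)
- Power without them, if power with them is 80% at two-sided 0.05: Φ((1.960 + 0.842)·√(1 − d) − 1.960)

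| Assumed d | SE ratio | SE larger by | Nominal 80% power becomes |
|---|---|---|---|
| 1% | 1.005 | 0.5% | 79.6% |
| 2% | 1.010 | 1.0% | 79.2% |
| 5% | 1.026 | 2.6% | 78.0% |
| 10% | 1.054 | 5.4% | 75.7% |

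The power column is for scale only, because this analysis has no power target.

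**Simulation check (all effects assumed)**

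The set-up was 600 patients, 1:1 allocation within the NYHA/age stratum, complete data and 1,500 replications. The true effect was 0.25 residual SD. NYHA III had 10% prevalence and effect −0.40; high NT-proBNP had 30% prevalence and effect −0.35.

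- Mean estimate: 0.248 without the factors and 0.249 with them, so no material bias either way.
- Mean SE: 0.0833 without and 0.0818 with, a ratio of 1.018.

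This agrees with the formula. The two factors contribute 0.40² × 0.1 × 0.9 + 0.35² × 0.3 × 0.7 = 0.0144 + 0.0257 = 0.0401 to the variance, so d = 0.0401/1.0401 = 3.9% and the ratio is √1.0401 = 1.020.

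**The case against.** The strongest objection is that the comparison that matters most cannot be made. The pattern-mixture analysis tests the primary MMRM against departures from missing at random, so it should share that model's covariates. The primary MMRM's terms (SAP 5.7.2.1.2) are redacted. If that model also omits the two factors, adding them in 9.4 alone would change two things at once. This stands, and it shapes the fix. For the same reason, a reader might infer that 9.4 departs from the primary model, but the public text cannot show that.

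A reader might also infer that an imputation model richer than the analysis model makes the combination invalid. It does not. Auxiliary variables in imputation are accepted practice, and any excess in the combined standard error is conservative. SAP 9.5 does the same: it imputes NYHA class using disease type and age, but the CMH analysis is not stratified by either.

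The omission may be deliberate for these endpoints. The subgroup MMRM for 6-MWT and KCCQ-OS in SAP 5.7.4 lists neither factor, while the composite, NYHA and recurrent-event subgroup analyses carry NT-proBNP. SAP 5.7 says how covariates are categorised; it does not require every model to hold all of them. This weakens any charge of inconsistency but does not supply a reason for the choice.

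Nor is the third stratification factor ignored. Everyone aged 75 or over falls in its second level whatever their NYHA class, and age group is in the ANCOVA. What remains unadjusted is the NYHA split below 75.

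Finally, the SE formula assumes complete data and is not Rubin's total variance. Pattern 1 values are drawn without regard to NYHA class or NT-proBNP, which dilutes the share the two factors can explain.

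**Conclusion.** The point holds as a minor one. The ANCOVA omits two available baseline factors, one of which helps define a randomisation stratum, and the SAP does not say why. The cost is modest precision: an SE about 0.5% to 5% larger for an assumed d of 1% to 10%, and 1.8% larger in the simulation. These figures rest on assumed effects and complete data, so they are an order of magnitude and not a prediction.

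A reader might go further and infer a biased estimate, a threat to Type I error control, or a serious risk that the check falsely suggests fragility. The documents support none of these. The estimate is unbiased with or without the terms, the testing procedure in SAP 4.6 gives no alpha to this sensitivity analysis, and an SE change of this size would rarely alter its reading.

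**What to change.** In SAP 9.4, add NYHA class (I/II vs III) and baseline NT-proBNP group (≤3000 vs >3000 ng/L) to the ANCOVA, in both the overall and monotherapy versions. Use the grouped NT-proBNP, as in the imputation model. A log-scale term would give the analysis model information that the imputation model lacks, and imputed values would not carry that relationship. Separate NYHA and age terms approximate the stratification factor without reproducing it exactly, which is adequate here.

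Keep the covariate set the same as in the primary MMRM, so that only the missing-data assumption changes. The sponsor can see that model. If it already holds both factors, the addition brings 9.4 into line. If it does not, treat the two models together, or state why both leave the factors out.

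The cost is two terms in one model statement, using values already collected and already used in the same appendix. The change should be made before unblinding for the primary analysis.
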